9.6 Special Situation Reports

Special situation reports include reports of overdose, misuse, abuse, medication error, and reports of adverse reactions associated with product complaints.

- **Overdose**: Refers to the administration of a quantity of a study drug given per administration or cumulatively (accidentally or intentionally), which is above the maximum recommended dose according to the protocol. Clinical judgment should always be applied. In cases of a discrepancy in the drug accountability, overdose will be established only when it is clear that the subject has taken additional dose(s) or the Investigator has reason to suspect that the subject has taken additional dose(s).
- **Misuse**: Refers to situations where the study drug is intentionally and inappropriately used not in a way that is not in accordance with the protocol instructions or local prescribing information and may be accompanied by harmful physical and/or psychological effects.
- **Abuse**: Is defined as persistent or sporadic, intentional excessive use of a study drug, which is accompanied by harmful physical or psychological effects.
- **Medication error**: Is any unintentional error in the prescribing, dispensing, or administration of a study drug by a healthcare professional, patient, or consumer, respectively. The administration or consumption of the unassigned treatment and administration of an expired product are always reportable as medication errors, cases of subjects missing doses of study drug are not considered reportable as medication error.
- **Product complaint**: Is defined as any written, electronic, or oral communication that alleges deficiencies related to the identity, quality, durability, reliability, safety, effectiveness, or performance of a drug or device after it is released for distribution. A special situations form will only be completed if a complaint is associated with an adverse drug reaction.

All special situation events as described above must be reported on the Special Situations Report form and faxed/mailed to Medpace Clinical Safety (contact information listed below) within 24 hours of knowledge of the event. All adverse events associated with these Special Situation reports should be reported as adverse events or SAEs as well as recorded on the adverse event eCRF and/or the SAE report form. Details of the symptoms and signs, clinical management, and outcome should be provided, when available.

Safety Contact Information:

9.7 Data Safety Monitoring Board

An independent data safety monitoring board (DSMB) will review cumulative unblinded safety data as outlined in the DSMB charter.

9.8 Evaluations for Safety

See [Section 7](#), Study Procedures for a description of various tests performed during this study. See [Appendix A](#) for a complete list of clinical laboratory analytes and Appendix A, Schedule of Events, for timing of various determinations.

10 STATISTICS

A detailed analysis plan will be described in a separate Statistical Analysis Plan (SAP). The SAP will supersede the protocol in the event of any differences between the 2 documents in the plans for data analysis, and the protocol will be amended if appropriate. The SAP will be included as an appendix in the clinical study report for this protocol.

10.1 General Design and Analysis

This is a randomized, double-blind, placebo-controlled Phase 2 study to assess the safety, tolerability, and efficacy of MAU868 for the treatment of BK viremia in kidney transplant recipients. The study will be conducted at approximately 20 clinical trial sites in the United States and Canada.

The Study includes a Screening Period (up to 10 days), a double-blind, placebo-controlled, randomized Treatment Period (12 weeks) and a Follow-up Period of 24 weeks.

Approximately 36 subjects will be randomized. Cohorts 1, 2 and 3 will randomize subjects to 1 of 2 treatment arms in a ratio of 2:1 (MAU868: placebo). Treatment groups within each cohort are:

Cohort 1

- MAU868 1350 mg IV q28 days for 4 doses
- Placebo (D5W) q28 days for 4 doses

Cohort 2

- MAU868 6750 mg Study Day 1 then 1350 mg IV q28 days for 3 doses (4 doses total)
- Placebo (D5W) q28 days for 4 doses

Cohort 3

- MAU868 6750 mg IV q28 days for 4 doses
- Placebo (D5W) q28 days for 4 doses

10.2 Determination of Sample Size

This study will randomize approximately 36 subjects (12 per cohort) to MAU868 and placebo in a 2:1 ratio (24 MAU868 and 12 placebo; 8 MAU868 and 4 placebo per cohort). This study is not powered to an efficacy endpoint. The number of subjects chosen will provide data useful in determining proof of concept.

10.3 Analysis Populations

The primary efficacy analysis will be performed in the modified ITT (MITT) analysis population. The MITT includes subjects who meet all of the following criteria:

- Received at least 1 dose of study drug.
- Has at least 1 post baseline plasma BKV PCR result available.

Additional analyses will be performed in the intent-to-treat (ITT) analysis population (all subjects randomized). The safety population will include all subjects who received at least 1 dose of study drug. The PK population will include all subjects with at least 1 post baseline PK sample available.

10.4 Safety Analysis

The primary objective of this study is to assess the safety and tolerability of MAU868 as measured by adverse events, vital signs (blood pressure, pulse rate, body temperature, oxygen saturation), ECG, and laboratory measurements.

10.5 Efficacy Analysis

Efficacy objectives of this study are secondary and include:

- To assess the impact of MAU868 on BKV related outcomes including viremia, BKV nephropathy, graft function and rejection among renal transplant patients with BK viremia

- To assess the pharmacokinetics of MAU868

Exploratory:

- To investigate the potential immunogenicity of MAU868
- To investigate genotypic resistance

10.5.1 Efficacy Endpoints

The efficacy endpoints for this study are:

- Time (weeks) to decrease of BKV plasma viral load by 1 log
- Time (weeks) to decrease of BKV plasma viral load to < lower limit of detection
- Proportion of subjects with > 1 log decrease of BKV plasma viral load at 1 week, 2 weeks, 4 weeks, 8 weeks, 12 weeks, and 36 weeks
- Proportion of subjects with BKV plasma viral load to < lower limit of detection at 1 week, 2 weeks, 4 weeks, 8 weeks, 12 weeks, and 36 weeks
- Rate of decrease in BKV plasma viral load over time.
- Change in eGFR from baseline to Week 12 and from baseline to Week 36 calculated using CK-EPI
- Proportion of subjects with BKV nephropathy
- Proportion of subjects with graft failure
- Proportion of subjects with acute rejection
- Survival

Exploratory:

- Presence of anti-drug antibodies (ADA)
- Presence of genotypic resistance

Statistical Methods

Efficacy Analyses

In all efficacy analyses, the placebo subjects from the cohorts will be combined. Thus, the analysis models will include treatment group (four levels: placebo, low dose, medium dose, high dose) as a factor. Time-to-event endpoints will be analyzed using Cox proportional hazards regression models. Proportion endpoints will be analyzed using logistic regression models. Quantitative endpoints will be analyzed using one-way analysis of variance (ANOVA) models. In all analyses, pairwise contrasts comparing each of the three active groups to the combined placebo group will be tested. All efficacy analyses will be conducted using two-sided tests at the alpha=0.05 level of significance, with no adjustment for multiplicity.

Additional efficacy analyses will be conducted using the data from each cohort. Quantitative endpoints will be analysed using the two-sample t test and proportion endpoints will be analysed using Fisher's exact test. Due to the small sample sizes, time-to-event variables will be summarized descriptively. Details of the data and process for the interim analyses will be described in the Statistical Analysis Plan and SSRC Charter.

Safety Analyses

All safety analyses will be performed on data from the Safety Analysis Population. Adverse events (AEs), vital signs, ECGs and clinical laboratory evaluations will be summarized by appropriate descriptive statistics.

Pharmacokinetic Analysis

MAU868 levels in serum will be determined by a validated ELISA-based method. A detailed description of the method used will be included in the PK bioanalytical data report. The anticipated LLOQ is 50.0 ng/mL. Concentrations will be expressed in mass per volume units (e.g., ng/mL). Missing values or those concentrations below the LLOQ will be labeled as such in the data listings and reported as "zero" in data presentations and calculations.

MAU868 serum concentration data will be listed by subject and visit/sampling time point. Descriptive summary statistics of trough levels will be provided by visit/sampling time point, including the frequency (n, %) of concentrations below the LLOQ and reported as zero. Summary statistics will include mean (arithmetic and geometric), SD, CV (arithmetic and geometric), median, minimum and maximum. Concentrations below LLOQ will be treated as zero in summary statistics.

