MAU868 levels in serum will be determined by a validated ELISA-based method. A detailed description of the method used will be included in the PK bioanalytical data report. The anticipated Lower Limit of Quantification (LLOQ) is 50.0 ng/mL. Concentrations will be expressed in mass per volume units (e.g., ng/mL). Missing values or those concentrations below the LLOQ will be labeled as such in the data listings and reported as "zero" in data presentations and calculations.

MAU868 serum concentration data will be listed by subject and visit/sampling time point. Descriptive summary statistics of trough levels will be provided by visit/sampling time point, including the frequency (n, %) of concentrations below the LLOQ and reported as zero. Summary statistics will include mean (arithmetic and geometric), SD, CV (arithmetic and geometric), median, minimum and maximum. Concentrations below LLOQ will be treated as zero in summary statistics.

Summary statistics (e.g., mean, standard deviation) and individual subject listing of serum concentration measurements of MAU868 at the assigned time points will be provided as surrogates of systemic exposure.

Interim Analyses

Separate from the blinded safety review by the SSRC which will enable enrollment of subjects into Cohort 2, unblinded safety and tolerability data (adverse events, clinical laboratories, vitals/physical exams and ECGs), efficacy data (BK viral load in the plasma) and PK (MAU868 plasma levels) will be reviewed by the SSRC once all 12 subjects in Cohort 1 have completed the treatment period. The treatment assignment in Cohort 1 will be unblinded; however, these data will not include associated subject or site identifiers. The objectives of this interim analysis

are to evaluate whether four doses MAU868 1350 mg IV administered every 28 days for a total of 4 doses demonstrate:

- safety and tolerability signals compared to placebo
- a decrease in BK viral load in plasma compared to placebo
- predicted MAU868 plasma levels

The conclusions from this first analysis will be used by the Sponsor to evaluate the safety and efficacy of MAU868 early-on in this first-in-patient study. Unless a significant safety issue related to administration of MAU868 has been identified, the conclusions will have no impact on Cohort 2 or the study's design.

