A first-in-human study explored single ascending doses of MAU868 (1, 3, 10, 30, and 100 mg/kg IV) and the serum concentration data was used to develop a PK model. The model was then used to estimate C_{trough} concentrations for a series of 3 treatment regimens. To have a treatment effect on BK viremia, MAU868 would need to curtail BKV replication in the target tissue (i.e., kidney). Based on an *in vivo* radiolabeled study in animals and PBPK modeling estimates, the antibody biodistribution coefficient in kidney is 13.7% (Shah and Betts 2013). The estimated trough levels for each treatment arm were compared directly to *in vitro*-determined antiviral activity (EC₅₀ and EC₉₀) for each BKV genotype and corrected for the assumed antibody distributions in kidney.

These data show that the planned dose regimens of MAU868 for each treatment arm provides high virus neutralizing tissue levels with kidney exposures at C_{trough} \geq 10-fold the EC₅₀ of the least susceptible BKV genotype (genotype III). Specifically, kidney exposures at C_{trough} range from 253 to 2618-fold (Cohort 1), 365 to 3775-fold (Cohort 2), and 1264 to 13,061-fold (Cohort 3) above the EC₅₀ at the end of treatment (12 weeks, range = least to most susceptible BKV genotype). Using EC₉₀ determinations, kidney exposures at C_{trough} range from 6 to 231-fold (Cohort 1), 8 to 333-fold (Cohort 2), and 28 to 1152-fold (Cohort 3) above the EC₉₀ at the end of treatment.

A 12-week treatment period was selected to ensure sustained levels of MAU868 to inhibit virus replication and promote virus clearance. The subsequent 24-week follow-up period will allow evaluation of the durability of effect and additional safety and PK observations.

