10.8.5 Pharmacokinetics

Population PK will be performed on all subjects. The PK analysis of MAU868 plasma concentration data will be performed using validated software in order to derive the population mean (and variance) values of specific PK parameters. Plasma concentrations will be summarized descriptively by time point of collection.

The PK endpoints for MAU868 are: area under the concentration-time curve to the end of the dosing period (AUC_{0-24}), area under the concentration-time curve up to the last measurable concentration ($AUC_{0-\text{last}}$), concentration at the end of infusion (C_{eoI}) and minimum concentration observed (C_{trough}). Plasma samples for pharmacokinetic (PK) evaluations will be collected at the time points described in the Schedule of Events ([Appendix A](#)).

Results of the PK analysis will be reported separately.

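### The protocol sets missing MAU868 concentrations to zero in calculations and asks for geometric statistics of data that may contain zeros, against its own narrower sentence and apparently against SAP 7.1.5

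*Protocol*

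**What the plan says.** The pharmacokinetic text in Protocol 10.5.1, repeated in the synopsis, contains four relevant statements.

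- Missing and below-LLOQ values are handled together: "Missing values or those concentrations below the LLOQ will be labeled as such in the data listings and reported as 'zero' in data presentations". The sentence then adds calculations to presentations.
- The statistics for troughs by visit are specified: "Summary statistics will include mean (arithmetic and geometric), SD, CV (arithmetic and geometric), median, minimum and maximum".
- A narrower sentence follows: "Concentrations below LLOQ will be treated as zero in summary statistics". It does not mention missing values. The frequency count requested just before it also covers only values below the LLOQ.
- The assay limit is given: "The anticipated LLOQ is 50.0 ng/mL".

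The SAP does not repeat the zero rule. SAP 7.1.5 ends by saying that missing values of variables other than those it has dealt with are not imputed and that only observed values are used. SAP 7.2.4, 7.6 and 8.2.3 send PK analysis to a standalone plan, which is not among the documents. Protocol section 10 gives the SAP precedence where the two differ, but the list of changes in SAP section 9 has no entry on PK.

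**The concern.** Zero is a proper entry for a measured concentration too low to quantify, at least in an arithmetic summary. It is a false entry for a sample that was never drawn, was lost or failed in assay. Missing samples are foreseeable. Under Protocol 3.3.2 and 8.1, a subject who stops study drug moves to follow-up visits, so the remaining pre-infusion troughs will not exist. The SAP also plans for pandemic-related non-completion.

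The geometric statistics raise a different problem: they fail outright instead of being biased. The logarithm of zero does not exist, and taken as a product the geometric mean is zero whatever the other values are.

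PK is a secondary objective. Agreement of drug levels with prediction is a stated aim of both interim reviews, and the second may lead to adjustment of the Cohort 3 regimen. A trough table that mixes real concentrations with zeros for absent samples would describe exposure wrongly to its readers.

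**Working it through.** The documents give no trough summary produced under this rule, so there is no stated figure to reproduce. The protocol's fold-multiples serve to check the inputs.

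**1. Predicted serum troughs.** Inputs are the kidney trough multiples of EC50 in Protocol 1.6 ("range from 253 to 2618-fold (Cohort 1), 365 to 3775-fold (Cohort 2), and 1264 to 13,061-fold (Cohort 3"), the genotype III EC50 of 0.093 µg/mL, the genotype I EC50 of 0.009 µg/mL and the kidney coefficient of 13.7%.

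Serum trough = fold × EC50 / 0.137, using the lower (genotype III) multiples:

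- Cohort 1: 253 × 0.093 / 0.137 = 171.7 µg/mL
- Cohort 2: 365 × 0.093 / 0.137 = 247.8 µg/mL
- Cohort 3: 1264 × 0.093 / 0.137 = 858.0 µg/mL

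Check against the upper (genotype I) multiples: fold × 0.093 / 0.009 gives 2614, 3772 and 13,061, against 2618, 3775 and 13,061 stated. The inputs agree within 0.2%.

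**2. Distance from the LLOQ.** 50.0 ng/mL is 0.05 µg/mL. The ratios are 171.7/0.05 ≈ 3,400, 247.8/0.05 ≈ 5,000 and 858.0/0.05 ≈ 17,200. A true below-LLOQ trough in a dosed active subject is therefore unlikely, leaving aside antibody-removing procedures (Protocol 5.3.1).

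**3. Arithmetic mean.** Protocol 10.2 gives "8 MAU868 and 4 placebo per cohort". With k of 8 values missing at random and entered as zero, expected mean = true mean × (8 − k)/8. For Cohort 1:

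| k missing | Mean, zero-filled (µg/mL) | Change | Mean, observed only (µg/mL) |
|---|---|---|---|
| 1 | 150.2 | −12.5% | 171.7 |
| 2 | 128.8 | −25% | 171.7 |
| 3 | 107.3 | −37.5% | 171.7 |

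If two samples were missing in Cohort 2 only, its mean would read 247.8 × 6/8 = 185.9, against 171.7 in Cohort 1. The predicted gap of 76 would shrink to 14 µg/mL.

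**4. Apparent CV.** Assume a true CV of 25%. The Phase 1 28-day levels in Protocol 1.4.2 have CVs from 12.7/171.3 = 7% to 145.9/509.8 = 29%. With population moments and divisor n − 1, CV² = (8/7) × [1.0625 × 8/(8 − k) − 1].

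- One missing: (8/7) × (1.0625/0.875 − 1) = 0.245, so CV ≈ 49%.
- Two missing: (8/7) × (1.0625/0.75 − 1) = 0.476, so CV ≈ 69%.

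This approximation runs slightly high: with none missing it gives 27%, and a lognormal simulation at 25% gives 48% and 68%. In simulations with other true CVs, one missing value raises the mean sample CV from 10% to 42% (true CV 10%), from 27% to 50% (29%) and from 37% to 57% (40%). At a true CV of 29% the median falls by about 5%.

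**5. Geometric mean.** One zero makes it 0, or undefined on the log scale. From observed values only it would be about 166 µg/mL in Cohort 1 (true CV 29%). Putting LLOQ/2 in place of a missing value does not repair it: (171.7⁷ × 0.025)^(1/8) ≈ 57 µg/mL.

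**6. How often.** The documents give no missing rate. At assumed rates of 2%, 5%, 10% and 15% per sample, the chance of at least one missing among 8 at a visit, 1 − (1 − p)⁸, is 15%, 34%, 57% and 73%.

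**The case against.** The strongest reply is that the rule may never reach a trough table. The sentence specific to summary statistics zeroes only below-LLOQ values. SAP 7.1.5 uses observed values only, and the SAP takes precedence. The PK plan may also say something different. Part of this stands: the documents conflict, and do not consistently require zero-filled trough means. But the broader protocol sentence expressly covers calculations, it is unclear whether SAP 7.1.5 reaches PK data that the SAP defers elsewhere, and SAP section 9 records no PK change. The vendor is left to choose.

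A reader might infer that both interim reviews are biased. The documents do not show that. SAP 8.1 supplies individual subject packages and profiles at the first interim, and missing values are labelled in listings. That review is also said not to affect the design unless a safety issue appears. For the second, SAP 8.2 again supplies profiles, and the PK output depends on the unseen plan.

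A reader might also infer that the Cohort 3 regimen would be set wrongly. That is not supported either. Cohort 3 may not exceed its planned dose. Against the protocol's own target of 10-fold the EC50, a 25% understatement leaves Cohort 1 at 253 × 0.75 ≈ 190-fold. SAP 7.6 derives PK parameters from compartmental fits to each subject's data, not from these descriptive means.

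Finally, zeros are not always missing samples. Day 1 pre-dose and placebo samples should be below the LLOQ, and zero is reasonable there in an arithmetic summary. The geometric statistics still fail for such data.

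**Conclusion.** The zero rule is wrong as written for missing values, and the documents contradict each other on it. Followed literally, it lowers an 8-subject mean trough by 12.5% for each missing sample, raises the CV from 25% to roughly 49% (one missing) or 69% (two), and leaves the geometric mean zero or undefined. The percentage changes in the mean are exact in expectation if samples are missing at random. The CV figures rest on an assumed true CV, and the chance of the problem arising rests on assumed missing rates.

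The consequence is limited to descriptive exposure summaries, including any shown at the second interim, and only if the PK plan does not override the rule. An effect on an interim decision is possible but not shown. This is a wording correction of moderate importance, not a threat to the primary safety objective.

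**What to change.** In Protocol 10.5.1 and the synopsis:

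- Remove missing values from the zero rule. State that they are labelled as missing in listings and excluded from calculations, with the number of observed values shown at each time point.
- Keep zero for below-LLOQ values in arithmetic summaries only.
- State one pre-specified rule for geometric statistics. One option is not to calculate them when any value is below the LLOQ and to show how many were. LLOQ/2 is another convention for measured below-LLOQ values, but a single such value can dominate the result and it must never stand in for a missing sample.

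Carry the same rule into the SAP, the PK analysis plan and the interim tables before the second interim review, and list it in SAP section 9 if the protocol is not amended. The cost is wording and table specifications; no new data are needed.

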10.6 Disposition, Demographics and Baseline Characteristics

Enrollment and randomization, protocol deviations, disposition and demographic data will be summarized and listed by treatment group. Continuous variables will be summarized by treatment group and combined using traditional statistics such as number of subjects, mean, median, standard deviation, minimum and maximum. Categorical variables will be summarized using frequency counts and percentages.

No inferential testing will be performed.

10.7 Concomitant Medications

Prior and concomitant medications will be identified using the most current version of the WHO Drug dictionary. The incidence of prior and concomitant medications will be summarized.

10.8 Safety

Adverse events, vital signs (blood pressure, pulse rate, body temperature), ECG intervals, laboratory results, and ADA results will be summarized and listed by treatment group.

10.8.1 Vital Signs

All vital signs data will be listed by treatment, subject, and visit/time and if normal ranges are available, abnormalities (and relevant orthostatic changes) will be flagged. Summary statistics will be provided by treatment and visit/time.

